MAGIPAC trial: Magnetic Resonance Imaging for Better Selection of Pancreatic Cancer Patients for Surgery: A Randomized Clinical Trial.

BACKGROUND AND SIGNIFICANCE

Pancreatic cancer has a dismal prognosis with a 5-year survival of only 8% [1]. Despite surgery being the only chance for cure, only 20% of the patients are eligible for surgical treatment, as most have metastatic disease at diagnosis [2]. Pancreatic cancer surgery is a major procedure with a substantial morbidity and mortality [3]. Therefore, it is important to avoid futile resections that will delay initiation of life-prolonging chemotherapy in patients who will not benefit from surgery. Whether the patient can be operated depends on the local extent of the tumor and the presence of distant metastases (most often in the liver), which are contraindications to surgery [4-6].

Currently, computed tomography (CT) is state-of-the-art for assessing pancreatic cancer resectability [7]. However, CT has some shortcomings. Although it performs well in assessing the local extent of the tumor, it has limited sensitivity for detecting small liver metastases in pancreatic cancer [8]. Relying solely on CT imaging therefore leads to futile resections in patients with undetected liver metastases. This will impair survival, as patients will have to recover from surgery and the associated complications before they can initiate chemotherapy. These shortcomings may be overcome by using liver and pancreatic magnetic resonance imaging (MRI) instead of CT.

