Upon consent, patients will be electronically randomized to one of the two treatment arms. Patients in the control arm will proceed directly to surgery. Patients in the intervention arm will have an MRI performed after randomization and before treatment. If the interval from CT to MRI is >14 days, a new CT will be performed to assure a valid comparator. The MRI will be read by an experienced gastro-radiologists blinded to the patient's identity and initial CT scan. Based on the MRI, the treatment decision will be made (*Figure 2*):

Figure 1. Study design. R: Randomization.

- 1) No liver metastases on MRI (expected ~75%): Surgery as planned.
- 2) Non-specific liver lesions on MRI, not seen on CT (expected $\sim 10\%$): Surgery as planned.
- 3) Liver metastases on MRI (expected ~15%): Referral to liver biopsy and oncological treatment if malignancy is verified. If biopsy is inconclusive, repeat liver MRI after one month.

[figure not shown]

Figure 2. Patient flow in the intervention arm. MDT: Multidisciplinary team conference.

Follow-up

Patients will be followed for up to three years for information on treatment, recurrence, and vital status. We will conduct standard-of-care follow-up CT at 3, 6, 9, 12, 18, 24, 30, and 36 months postoperatively in all patients. Primary end-point for this project will be one-year survival. For subsequent studies, we will also perform analyses of three-year survival.

SPECIFIC STUDY AIMS, HYPOTHESES AND OUTCOMES

Study I: To compare tumor staging of pancreatic cancer patients assessed by MRI versus upper abdominal CT.

Study II: To assess the ability of MRI to detect liver metastases in pancreatic cancer patients with resectable tumor on CT.

Study III: To assess the impact of MRI on treatment allocation, recurrence, and survival in pancreatic cancer patients with a resectable tumor on CT.

Details of study hypotheses, population, and analytical plans are outlined in Figure 3.

	Study I	Study II	Study III
Aim	To compare tumor	To assess the ability of	To assess the impact of
	staging of pancreatic	MRI to detect liver	MRI on treatment
	cancer patients assessed	metastases in pancreatic	allocation, recurrence,
	by MRI versus upper	cancer patients with	and survival in pancreatic
	abdominal CT	resectable tumor on CT	cancer patients with a
			resectable tumor on CT
Hypothesis	MRI is non-inferior to CT	MRI will detect liver	Use of MRI will change
	with respect to tumor	metastases in patients	treatment allocation and

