	staging	with a resectable tumor	improve overall survival
		on CT	
Population	Patients in the	Patients in the	Patients in both arms
	intervention arm (N=100)	intervention arm (N=100)	(N=200)
Analysis	Agreement assessed by	Agreement assessed by	Treatment allocation and
	intraclass correlation	intraclass correlation	recurrence by Chi ² test
	coefficient (ICC)	coefficient (ICC)	Survival analyses by
			Kaplan-Meier estimation

Figure 3. Outline of the three studies.

POWER CALCULATIONS AND FEASIBILITY

Assuming alpha=0.05, power of 80%, and a hazard ratio of death of 1.5, we need 191 patients in total. To guard against dropout of 5%, we aim to include 200 patients. On average, all four institutions performing pancreatic cancer surgery in Denmark (Rigshospitalet, Aarhus, Aalborg, and Odense) shall include 50 patients. We aim to finalize patient enrollment during the first 18 months of the study period, equaling to 2.8 patients monthly in each institution. In total, ~300 resections will be performed during this 18-month period. We consider it feasible and realistic to include two-thirds of these patients.

IMAGING PROTOCOLS

CT imaging protocol

As a part of the routinely workup for staging pancreatic cancer, all patients referred to the local hepato-pancreato-biliary MDT board undergo a pancreas-specific CT scan. All CT scans include a

portal venous phase (PVP) of the liver. CT scanners from different vendors will be used to acquire the images. The PVP will routinely obtained by 120 KV and mAs range from 150 to 290 depending of the body mass of the patient and the scan system. Contrast medium will be administered intravenously as a bolus injection by weight bases contrast Iodine concentration of 500 – 750 mg I/kg and a rate of 3-5 ml/s, followed by a saline flush of 20–40 ml. The scan delay for the PVP will be 50 sec (post-threshold, bolus tracking). Axial slice thickness of 2 mm slices will be reconstructed with 1 mm increments.

MR imaging protocol

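### Study III's recurrence Chi-square leaves the event, the time point and unresected patients undefined; if recurrence means return of disease after resection, the N=200 comparison favours MRI even with no reduction in disease or death

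*Combined protocol and SAP*

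**What the plan says.** Recurrence is one of three outcomes in the aim of Study III. Its analysis is a single entry in Figure 3, shared with treatment allocation: "recurrence by Chi"-square test. The Population row for Study III reads "Patients in both arms", N=200.

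The two pathways differ (Study design and patient flow). For controls: "Patients in the control arm will proceed directly to surgery". For the MRI arm: "Liver metastases on MRI (expected ~15%): Referral to liver biopsy and oncological treatment if malignancy is verified". If the biopsy does not settle the matter: "If biopsy is inconclusive, repeat liver MRI after one month".

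Under Follow-up: "Patients will be followed for up to three years for information on treatment, recurrence, and vital status". The scan schedule is: "We will conduct standard-of-care follow-up CT at 3, 6, 9, 12, 18, 24, 30, and 36 months postoperatively in all patients". The one-year time point is attached to survival only.

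The text reviewed does not say what counts as a recurrence, from which date or to which date it is counted, or how a patient without a resection enters the table.

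**The concern.** A Chi-square on recurrence is neutral between arms only if patients in both arms can have the event under the same rules. Here the intervention decides, after randomisation, who is resected. If recurrence has its usual meaning of return of disease after resection, a diverted MRI-arm patient cannot have one. A control patient with the same metastases who is resected can. The follow-up CT schedule does not resolve this: it is counted from surgery yet stated for every patient, so it has no starting date for those not operated on.

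At stake is a secondary result of Study III that could show fewer recurrences with MRI although neither disease nor death has been reduced. The misreading is a live risk. The Background cites a retrospective study in which operated patients who had had an MRI recurred later, and takes this as a hint of benefit while doubting that it generalises.

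**Working it through.** **Plan's own figure.** There is none for recurrence. The only calculated figure is 191, for survival at a hazard ratio of 1.5. The Schoenfeld formula reproduces it (two-sided 0.05, 80% power, 1:1) as 4 × (1.960 + 0.842)² / (ln 1.5)² = 191. It has no bearing on recurrence.

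**Inputs from the documents.** 100 patients per arm. M, the share with liver metastases on MRI, is about 15% as planned; the Background cites 5% and almost 25% from two studies. M is an upper bound for the share diverted, because verification is required.

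**Assumed inputs (not in the documents).**
- q = 80-100%: recurrence in resected patients with occult metastases.
- r = 30-60%: recurrence in other resected patients.
- v: share of MRI-positive patients verified and diverted.
- h: share of operated occult metastases found at operation, left unresected and not counted.
- Unverified MRI-positive patients are taken as metastatic and operated on.
- MRI changes neither disease nor death.

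**Formulas, under the usual meaning of recurrence.**
- All randomised: control = (1−h)Mq + (1−M)r; MRI = (1−h)(1−v)Mq + (1−M)r. The false difference is (1−h)vMq.
- Resected only: the same numerators, divided by 1−hM (control) and 1−vM−h(1−v)M (MRI). With v=1 and h=0 the false difference is M(q−r).

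**Example, M=15%, q=1, r=0.4.**
- v=h=0.5: control 0.075 + 0.34 = 41.5%; MRI 0.0375 + 0.34 = 37.75%; difference 3.75 points.
- v=1, h=0: control 0.15 + 0.34 = 49%; MRI 34%. As 49/100 against 34/100, Chi-square = 200 × (49×66 − 34×51)² / (100×100×83×117) = 4.63, p=0.031. Yet each arm has 51 patients resected and recurrence-free (100−49 and 85−34).

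**Chance of a significant result favouring MRI.** Exact binomial enumeration, Pearson Chi-square, two-sided 0.05, so nominally 2.5% in this direction. M=15%:

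| Scenario | All randomised | Resected only |
|---|---|---|
| All verified, no control metastases found at operation (v=1, h=0) | 41.6-62.2% | 6.2-31.8% |
| Half verified (v=0.5, h=0) | 13.9-19.8% | 3.5-10.3% |
| Half found at operation (v=1, h=0.5) | 13.9-21.5% | 4.8-12.5% |
| Both halvings (v=h=0.5) | 6.4-8.4% | 3.4-5.7% |
| All found at operation (h=1) | 2.5-2.8% | 2.4-2.7% |

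For all randomised, the expected false difference is 12-15 points in the first row and 3-4 points with both halvings. From both halvings up to the first-row scenario, M=5% gives 3.5-4.1% up to 8.5-11.7%, and M=25% gives 10.9-15.8% up to 82.6-96.5%.

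**Does the resected-only tilt depend on q exceeding r?** Yes. At M=15%, v=1, h=0 (85 against 100 patients):
- q=r=0.8: 0 points, 2.6% favouring MRI.
- q=0.95, r=0.8: 2.2 points, 6.0%.
- q=0.5, r=0.6 (for example, death before recurrence is recorded): −1.5 points, with 1.5% favouring MRI and 4.0% favouring control.

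**The case against.** Four objections have force.

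1. A reader might infer that the recurrence test has no denominator at all. The documents do not support that: Figure 3 gives N=200 for Study III. What is missing is how unresected patients count within it. This does not rescue the analysis, because N=200 is the more biased of the two denominators when diverted patients score as recurrence-free. Restricting to resected patients would be a departure from the stated population.

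2. A reader might infer that any choice of denominator must favour MRI. For resected patients only, this needs higher recurrence with occult metastases than without. The Background makes that plausible ("Relying solely on CT imaging therefore leads to futile resections in patients with undetected liver metastases") but gives no rate. Follow-up runs to as much as three years, so high recurrence in both groups cannot be excluded. The assumed ranges keep q above r, so they build in the direction.

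3. A reader might conclude that no patient gains anything. The Future perspectives section names avoided surgery as a benefit, and diverted patients do avoid it. The false signal concerns disease and death only.

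4. The size is uncertain. The largest figures need every MRI-positive patient verified and no control metastasis found at operation. Recurrence is also absent from Study III's hypothesis, which names treatment allocation and overall survival.

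The objections narrow the claim and reduce its likely size. They do not touch the all-randomised comparison under the usual meaning of recurrence, where the direction follows from the pathway unless every control metastasis is found at operation and left uncounted.

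**Conclusion.** The concern holds in this form. The plan specifies a test without an event definition, time origin, time point or rule for unresected patients. If recurrence means return of disease after resection, the stated N=200 comparison favours MRI with no reduction in disease or death. A resected-only comparison also favours MRI if recurrence is higher in occult-metastatic than in other resected patients; that tilt is nil at equal rates and can reverse.

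At 15% MRI-positive, the chance of a false significant advantage runs from 6-8% (both halvings) to an upper bound of 42-62% for all randomised, and from 3-6% to 6-32% for resected only. These figures rest on the assumed recurrence, verification and operative-detection rates. Both tilts vanish if all control metastases are found at operation, left unresected and not counted. They are also removed if metastases found before or at surgery count as events; the plan does not say that they do.

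It would be wrong to read this as a threat to the main result: one-year survival and the treatment-allocation comparison are unaffected. The point should be fixed before analysis.

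**What to change.** Replace the recurrence Chi-square with a comparison of all randomised patients, from randomisation to one fixed cut-off. The cut-off is the same in both arms and late enough to include the 12-month postoperative CT (for example, 12 months plus a stated number of weeks). For unresected patients, use whatever imaging and clinical records exist. Count as an event, alike in both arms: verified metastatic or unresectable disease found before or at surgery, recurrence, or death. Non-resection for other reasons is not an event in itself. Report the risk difference with its 95% CI, and report recurrence among resected patients descriptively only, as a measure of selection.

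**Cost.** SAP wording, plus a data field for metastatic or unresectable disease found at operation if none exists. Treatment, recurrence and vital status are already collected, and no patients, scans or visits are added. Inclusion is planned over the 18 months from January 2022, so 12 months from the last randomisation falls in mid-2024. That leaves room for the added weeks before the project ends in December 2024.

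**Downside to state in the SAP.** This is a composite that overlaps survival and does not credit MRI for avoided surgery. It can tilt slightly against MRI, because every diverted patient is an event while some controls with occult metastases may have no recorded event by the cut-off. If up to 20% have none (q=0.8) and h=0, the tilt is vM(1−q):
- 15% diverted: up to 0.15 × 0.20 = 3 points, significantly favouring control in up to 6.8% of trials with no true difference (nominal 2.5%).
- 25% diverted: up to 0.25 × 0.20 = 5 points, up to 11.5%.

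Precision is limited: at rates near 50%, the 95% CI is about ±1.96 × √(2 × 0.25/100) = ±14 points.

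### Survival analysis is specified only as Kaplan-Meier, with no between-arm test, baseline adjustment or account of institution, and stratification of the randomisation by institution is not stated

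*Combined protocol and SAP*

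**What the plan says.** Under Follow-up, the primary endpoint is survival at one year; patients are followed for up to three years, and three-year survival is left to subsequent studies. In Figure 3, the Study III analysis cell assigns a chi-squared test to treatment allocation and recurrence. For survival it gives only "Kaplan-Meier estimation".

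On allocation, the section Study design and patient flow says: "Upon consent, patients will be electronically randomized to one of the two treatment arms". The Patients section gives 100 per arm. Neither names a stratification factor, a block scheme or minimisation.

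On what is known beforehand, the CT imaging protocol states that "all patients referred to the local hepato-pancreato-biliary MDT board undergo a pancreas-specific CT scan". The Patients section restricts entry to tumours judged resectable on CT. The power section begins a sentence "On average, all four institutions performing pancreatic cancer surgery in Denmark" and sets an average of 50 patients for each.

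On size, the same section reads "Assuming alpha=0.05, power of 80%, and a hazard ratio of death of 1.5", then "we need 191 patients in total", then "To guard against dropout of 5%, we aim to include 200 patients".

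**The concern.** Kaplan-Meier is an estimator of a survival curve. It does not compare two arms. The same table cell names a test for the other Study III outcomes, so the primary endpoint is the one left without a test or an effect measure. The choice between a log-rank test, a Cox model and a comparison of one-year proportions, and the choice of any covariates, would be open after the data are seen.

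Two baseline items are also left unused. The four institutions have their own tumour boards, radiologists and scanners, and may differ in outcome. The eligibility CT precedes randomisation in everyone. If either predicts death, an analysis that ignores it gives up some power. If allocation is not stratified by institution, the arms can be visibly uneven within a hospital. That invites doubt about a result that is likely to be imprecise anyway.

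**Working it through.** **1. The plan's own figure.** Inputs from the power section: alpha 0.05, power 80%, hazard ratio 1.5; allocation 1:1. Schoenfeld's formula, two-sided:

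deaths = 4 × (1.960 + 0.842)² / (ln 1.5)² = 4 × 7.849 / 0.1644 = 191.

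This matches the plan exactly (one-sided gives 151; Freedman's formula gives 197). The result is a count of deaths, whereas the plan calls it patients. Inflating for 5% dropout gives 191 / 0.95 = 201.05, rounded up to 202, close to the stated 200.

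**2. Power available at one year.** No survival rate is given, so overall one-year survival of 60%, 70% or 80% is assumed. Power = Φ(√D × ln 1.5 / 2 − 1.96), where D is the number of deaths among 200 patients:

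- 60%: D = 80, power 44%
- 70%: D = 60, power 35%
- 80%: D = 40, power 25%

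**3. Gain from adjustment and stratified analysis.** Prognostic strength is not in the documents. Assumptions: 200 patients, four sites of 50, totals fixed at 100/100 without site stratification, and a true hazard ratio of 1/1.5 in favour of MRI. Control one-year survival is 60% or 70% at average covariates. There is one 50:50 baseline factor with hazard ratio 1 to 3, and adjacent sites differ by 0.15 in log hazard (no site effect in the hazard ratio 1 row). There were 1,500 simulated trials per row, with simulation error of about 1.3 points per power figure. The longer horizon of 18 to 36 months follows from a 36-month project with enrolment in the first 18. Each cell shows power from an unadjusted Cox model → power from a Cox model stratified by site and adjusted for the factor.

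| Control one-year survival | Factor HR | 12-month censoring | 18–36 months |
|---|---|---|---|
| 60% | 1 | 40.3 → 39.1 | 58.1 → 57.1 |
| 60% | 1.5 | 36.8 → 36.7 | 58.3 → 57.9 |
| 60% | 2 | 35.2 → 36.9 | 53.8 → 58.7 |
| 60% | 3 | 36.1 → 39.5 | 48.1 → 57.9 |
| 70% | 1 | 29.7 → 28.7 | 49.5 → 48.7 |
| 70% | 1.5 | 30.5 → 30.9 | 47.5 → 47.6 |
| 70% | 2 | 27.1 → 27.7 | 47.9 → 50.5 |
| 70% | 3 | 29.2 → 31.0 | 44.1 → 50.1 |

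A separate check at 70% used a single prognostic score with SD 0.3, 0.5 or 0.7 on the log-hazard scale. It gave changes of about −1, +2 and +5 points at 12 months, and +1, +4 and +8 at 18 to 36 months. For scale, a 50:50 factor with hazard ratio h has SD ln(h)/2. Hazard ratio 3 therefore corresponds to 0.55, and SD 0.7 needs exp(1.4), about 4.

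**4. Imbalance within institutions, if allocation is not stratified by site.** Each site is taken at the stated average of 50.

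- Simple randomisation: 2 × P(X ≥ 30), X ~ Binomial(50, 0.5), = 0.203 for a 30:20 split or worse at a given site. For at least one of four sites: 1 − (1 − 0.203)⁴ = 0.596.
- Totals fixed at 100/100: the hypergeometric probability for one site is 0.141. For at least one of four it is 0.405 (40,000 simulated allocations).

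**The case against.** An unadjusted comparison of randomised arms is valid, and three stronger readings go too far.

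- **That the randomisation is unstratified.** A reader might infer this from the one-sentence description. The text neither states nor excludes stratification, and an electronic system could well include it. The imbalance probabilities are therefore conditional, and the planned 100 per arm is at least compatible with restricted allocation.
- **That hospital differences could pass for an MRI effect.** Chance imbalance by site does not bias a randomised comparison on average, and the test's type I error already allows for it.
- **That a worthwhile amount of power is being thrown away.** The larger gains need both strong covariates and follow-up beyond the one-year endpoint. Entry is limited to CT-resectable tumours, which narrows the range of stage and may limit the gain further.

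These objections stand against the stronger readings. One practical objection also stands in part. The documents show that every patient has a CT, but not that a stage is recorded from it in both arms: the CT staging comparison in Study I covers the intervention arm only. Age is not named as a collected variable.

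The objections do not touch the omission itself. The plan has no between-arm survival analysis, and the method proposed here costs almost nothing.

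**Conclusion.** The point holds in a limited form. The primary endpoint has no stated between-arm analysis, available baseline information goes unused, and the role of institution in the randomisation is not stated. A prespecified analysis stratified by institution and adjusted for baseline factors is the better choice. Its benefit is modest and conditional: about 0 to 5 power points at one year over the assumed range, about 8 to 10 at most with 18 to 36 months of follow-up, and a loss of about 1 point if the covariates carry no information. All of these rest on assumed control survival, covariate strength and site differences.

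Within-site imbalance of 30:20 or worse in at least one hospital would have probability 60% under simple allocation, or 40% with fixed totals. The consequence is lost precision and credibility, not bias.

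A reader might infer that adjustment makes up for the trial's size. It does not. Power of roughly 25% to 44% at one year comes from treating 191 deaths as 191 patients, and a few points do not close that gap.

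**What to change.** In the analysis plan:

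1. Make the primary between-arm survival comparison a Cox model stratified by institution and adjusted for age and tumour stage on the eligibility CT. Truncate follow-up at 12 months for the one-year endpoint.
2. Take stage from the eligibility CT only. The repeat CT, done when the CT-to-MRI interval exceeds 14 days, occurs only in the MRI arm and must not serve as a covariate.
3. Keep Kaplan-Meier curves as the display and an unadjusted log-rank test as a sensitivity analysis.
4. State the randomisation method. If it is not already stratified and enrolment permits, use permuted blocks of random size, stratified by the four institutions.

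The cost is one paragraph in the plan and, where needed, one setting in the randomisation system. There are two small downsides: age and eligibility-CT stage must be recorded in both arms, and the adjusted hazard ratio is conditional on the covariates, which the report should say. If enrolment has begun, items 1 to 3 can still be adopted, provided they are fixed before outcomes are compared by arm. The sample size needs separate correction.

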The MRI will be performed using 1.5 or 3.0 T MR scanners of different vendors. The liver will be scanned using axial and coronal T2W single shot (SS) TSE, axial DWI (minimum b-values of 50 and 800) and axial T1W 3D spoiled gradient echo for gadoxetic acid (Primovist, Bayer Pharma, Berlin, Germany) contrast scans. Both a dynamic contrast scan consisted of; pre-contrast phase, arterial phase (timed using bolus tracking) followed immediately by porto-venous phase; late phase at 2 min and hepato-biliary phase 15 min after contrast injection. The gadoxetic acid contrast will be injected at 1 or 2 mL/s depending of using a dilution 1:1 of gadoxetic acid and saline 9mg/ml or not. The dose will be 0.025 mmol/kg body weight with a maximum of 2.5 mmol using a power injector.

Analysis for metastatic lesions

Each modality will be read anonymized. Both CT and MRI images will be read independently by dedicated radiologist from each participating site as part of the routine work-up in staging pancreatic cancer. The CT scan will be performed as the first examination followed by MRI scan within 14 days after the CT scanning. For all focal hepatic lesions confidence of malignancy will be categorized via a 3-point scale, 1: benign, 2: indeterminate, 3: malignant.

FEASIBILITY

Time schedule

The project will begin in January 2022 and end in December 2024. We will include the patients within the first 18 months of the project period. In the final year of the study period, we will perform data analyses and writing of scientific papers. This will allow for a sufficient follow-up period of all patients (please see *Figure 4* for detailed time schedule).

[figure not shown]

Figure 4. Time schedule.

Scientific and non-scientific personnel

At each institution, one research nurse will be responsible for identification of potential study subjects and, in collaboration with the surgeon, perform the practical work on obtaining informed consent and randomize the patients. The research nurse will also be responsible for each patient's path through the project, *e.g.* schedule the imaging and collect data, and to coordinate the project with the research nurses at the other participating sites.

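### The 191 patients in the power calculation equals the number of deaths needed, so 200 patients do not give 80% power for one-year survival

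*Combined protocol and SAP*

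**What the plan says.** The combined protocol and SAP has one sample-size calculation, under Power calculations and feasibility: "Assuming alpha=0.05, power of 80%, and a hazard ratio of death of 1.5, we need 191 patients in total". It continues: "To guard against dropout of 5%, we aim to include 200 patients". It names no test, sidedness, number of deaths, control survival or time horizon.

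Under Follow-up the end-point is set: "Primary end-point for this project will be one-year survival". Patients are followed for up to three years, but the three-year survival analysis is left to later studies. The design section gives 100 patients per arm, all with CT-assessed resectable disease and allocated to surgery. Figure 3 assigns the survival comparison to Study III, with both arms and Kaplan-Meier estimation.

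On available patients, the power section says: "In total, ~300 resections will be performed during this 18-month period".

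**The concern.** Power to detect a hazard ratio depends on the number of deaths. A significance level, a power and a hazard ratio fix how many deaths are needed. To turn that into patients one also needs the proportion expected to die by the analysis, and the protocol gives none. If 191 is a death count used as a patient count, the calculation assumes in effect that every patient dies within follow-up.

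This is the only justification for enrolling 200 patients, and it concerns the primary end-point. The funder and the ethics committee are told 80%. If the true figure is much lower, a non-significant result could be misread as evidence that preoperative MRI does not affect survival.

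**Working it through.** **Inputs from the documents.** Alpha 0.05, power 80%, hazard ratio 1.5, dropout 5%, total 200 (Power calculations and feasibility); 1:1 allocation (Patients); end-point at one year (Follow-up). Sidedness is not stated. Two-sided is used because, with the stated inputs, it reproduces the plan's figure.

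**Reproducing 191.** Deaths = 4 × (1.960 + 0.8416)² / (ln 1.5)² = 190.97, rounded up to 191. A hazard ratio of 1/1.5 gives the same number. Other formulas do not match: Freedman two-sided gives 197, Schoenfeld one-sided 151, Freedman one-sided 155. A two-sided comparison of one-year proportions under a hazard ratio of 1.5 needs at least 302 patients at any control survival.

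**What 191 deaths would require.**
- 191 / 200 = 95.5% of patients dead at the analysis.
- After 5% dropout, 200 × 0.95 = 190 patients remain. If all 190 died, power would be 79.8%.
- At one year with a hazard ratio of 1.5, 191 deaths among 200 needs 98.1% mortality in the control arm and 92.9% in the MRI arm.
- For scale, the background section puts five-year survival at 8% for pancreatic cancer overall, most of it metastatic at diagnosis. That is about 92% dead at five years.

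**Power at one year.** The documents give no mortality for resectable patients, so control one-year mortality *m* is assumed over a range.
- MRI-arm mortality = 1 − (1 − m)^(1/1.5)
- Deaths D = 100 × (sum of the two mortalities)
- Power = Φ(½ √D × ln 1.5 − 1.96)
- The hazard ratio detectable with 80% power solves ½ √D × ln HR = 2.80, with D recalculated at each HR
- Patients needed = 190.97 / mean mortality of the two arms

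| Assumed control mortality | 20% | 30% | 40% | 50% | 70% |
|---|---|---|---|---|---|
| MRI-arm mortality | 13.8% | 21.2% | 28.9% | 37.0% | 55.2% |
| Deaths among 200 | 34 | 51 | 69 | 87 | 125 |
| Power, 200 patients | 22% | 30% | 39% | 47% | 62% |
| Power, 190 patients | 21% | 29% | 37% | 45% | 60% |
| HR detectable with 80% power | 2.9 | 2.3 | 2.0 | 1.9 | 1.7 |
| Patients needed for 191 deaths | 1,130 | 750 | 555 | 440 | 305 |

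A two-proportion test at one year gives nearly the same power: 21%, 30%, 38%, 46% and 58%.

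**Longer follow-up.** This assumes exponential survival, uniform accrual over 18 months and the same five mortalities.

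| Power at assumed control mortality of | 20% | 30% | 40% | 50% | 70% |
|---|---|---|---|---|---|
| Cut at end of 2023 (6 to 24 months' follow-up) | 25% | 35% | 44% | 52% | 66% |
| Cut at end of December 2024 (18 to 36 months) | 38% | 51% | 60% | 68% | 76% |
| Three full years for every patient | 46% | 59% | 68% | 73% | 79% |

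**The case against.** **The origin of 191 is inferred.** The protocol names no formula. This stands: the accurate wording is that 191 equals the two-sided Schoenfeld death count. One alternative can be constructed, a one-sided test needing 151 to 155 deaths with 79% to 81% of 191 patients dying, but the documents state neither condition. A one-sided test with 200 patients gives only 32% to 73% power at one year over the assumed range. The conclusion on power does not depend on how 191 arose.

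**The power sentence has no time horizon, and follow-up runs to three years.** This is fair, and at 70% one-year mortality the three-year power of 79% is practically the stated value. At 20% to 50% mortality it is still only 46% to 73%. The protocol also places the primary end-point at one year, and with 18 months of accrual and a project end in December 2024, patients enrolled late cannot reach three years within the project.

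**More patients could be recruited.** At 20% to 50% mortality this clearly fails: 300 patients would give 30%, 43%, 54% and 64%. At 70% it would come close, at 79.3%, but only by enrolling a number equal to all the resections expected in the accrual period. That count is of resections, not of eligible patients, so the comparison is approximate.

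**The mortality range is assumed.** It is, because the documents give none. The comparison with five-year survival also needs the premise that resectable patients do no worse than all patients. That is reasonable, since the background calls surgery the only chance of cure, but it is a premise. The 95.5% requirement needs no such assumption.

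**Conclusion.** The concern holds. The stated inputs determine 191 deaths, and the protocol reports that number as patients. The 80% power is therefore not a property of the design for its primary end-point. At one year it is roughly 20% to 60% for control mortality between 20% and 70%, and the hazard ratio detectable with 80% power lies between about 2.9 and 1.7 rather than at 1.5.

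The death requirement rests only on the protocol's inputs, two-sided testing and 1:1 allocation. The power figures also rest on the assumed mortality and on proportional hazards. The error is confined to the survival comparison in Study III. It must be corrected because it is the only stated basis for the sample size.

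**What to change.** 1. **Replace the power sentence**, for example with: *With two-sided alpha 0.05, 1:1 allocation and a hazard ratio of death of 1.5, 191 deaths are needed for 80% power. With 200 patients and an assumed control one-year mortality of X%, about D deaths are expected at one year, giving power of P%; the hazard ratio detectable with 80% power is H.* The sponsor supplies X with its source; D, P and H follow from the formulas above.
2. **State how the result will be reported**: a hazard ratio or one-year survival difference with a 95% confidence interval, and no reading of a non-significant result as absence of benefit. The protocol does not claim otherwise, but the low power makes this worth writing down.
3. **Optional, with the primary end-point unchanged**: add a supporting log-rank or Cox analysis using all follow-up to the data cut. The cut date must be fixed, because the time schedule says only: "In the final year of the study period, we will perform data analyses and writing of scientific papers". At 20% to 40% control mortality the gain over one year is 4 to 5 percentage points for a cut at the end of 2023 and about 17 to 21 points for a cut at the end of December 2024. Neither restores 80%.

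Items 1 and 2 are wording only, with no extra patients or visits. Their cost is a visibly weaker power statement that the funder or ethics committee may question. Item 3 adds one analysis of vital-status data already being collected.
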